E) Mailing labels will be generated for patients seen by [name] between January 2022 and January 2023 with ICD code of G20 and who identified as Hispanic/Latino. A letter from [name] office will be included in this mailing. Other patients within the UConn Health Center system that also have the ICD code of G20 but are not patients of [name] will receive a mailing notifying them of the study from their treating physician's office. Interested participants will be interviewed for eligibility and those who offer written, informed consent will be enrolled.

F) We will also work with Clinical Research IT at UConn Health to identify eligible individuals seen at UConn Health and make them aware through their MyChart account that they may be eligible for participation in the study

Phone Screen

We will conduct a telephone screening to provide interested persons with more information about the study involvement and conduct a pre-consent telephone eligibility screening to see if they qualify.

Inclusion Criteria

Idiopathic Parkinson disease, able to walk without the assistance of another person for 10 minutes, ≥ 29 on Telephone Interview for Cognitive Status (TICS), has a close friend/family member over the age of 18 that would support the participant during the intervention, ≥ 50 years of age, Hispanic, willing to use an activity tracker, on a stable course of PD medications without any plans for change over the next 3 months, able to speak, read and write in Spanish or English, currently live in the United States or US Territory (*Puerto Rico, U.S. Virgin Islands, Guam*).

Exclusion Criteria

Unstable cardiopulmonary, orthopedic, psychological or metabolic condition, Atypical Parkinsonism Disorders, a fall in the last 6 months (that was unrelated to an external force), currently engaging in 150 minutes of mod-vigorous physical activity/week

Study Enrollment Procedures

A HIPAA waiver will be obtained from the IRB to collect personal information over the telephone. Following a phone screen, participants will be sent a link, through email or text message, to an online consent form or receive the consent form via standard mail. (see below for additional details on the consent process)

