Study Procedures: All study procedures will be conducted in the preferred language of the participant (English or Spanish). All participant-facing written and spoken study materials will be available in English or Spanish. Study materials will be translated and back translated by study staff members. Participants will be able to self-select which language to set on their phone or tablet. Their preferred language will automatically be programmed for the application used in the study.

- Screening Procedures: Interested individuals will call or email the lab. A research assistant (bilingual) will respond to their interest by telephone call or email and will establish a mutually agreeable date and time for the telephone screening. The telephone screening will assess basic information (age, ethnicity, verbal confirmation of physician diagnosis of Parkinson's disease and ability to walk for 10 minutes without the assistance of another person) and includes a screening of cognition (Telephone Interview for Cognitive Status (TICS)) and Physical Activity Readiness (PAR-Q). Additionally, individuals will be asked about their medical history, current medications, willingness to wear an activity monitor and use the FitBit app, ability to speak, read and write in Spanish or English, current involvement in exercise and the availability of a family member (≥ 18 years of age) to support their participation in the study. (approximately 30-40 minutes)

Those that are:

- ≥ 50 years of age
- Hispanic/Latinx
- Diagnosed with idiopathic Parkinson's disease (by self or family-report)
- Indicates that there is a close friend/family member ≥ 18 years of age that can support their participation in the study
- self-report the ability to walk 10 minutes without the assistance of another person
- score ≥ 29 on the TICS
- are willing to wear an activity monitor and use a FitBit and the FitBit application
- able to speak, read, and write in Spanish or English
- on a stable course of PD medications without any plans for change in the next 3 months

will be invited to participate in the study.

- Study Procedures: Once interested individuals have passed the telephone screening, they will be sent a link, through email or text message, to an online consent form or receive the consent form via standard mail. (Consent procedures are detailed further below)

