 8. **Lille Apathy Rating Scale (LARS)**:³² This is a 33-item structured interview that was designed to assess apathy in Parkinson's disease. It is suggested scale for use in people with PD by the Movement Disorder Society.³³ (approx. 15-20 minutes to complete)
 9. **Sallis Support Scale for Exercise Survey**:³⁴ This is a survey with 5 items focused on perceptions of social support from friends and 15 items for family regarding exercise behavior. It

has reported reliability of 0.86-0.90 and internal consistency of 0.86-0.89.³⁵ (approx. 10 minutes to complete)

10. Participants will be sent a research-grade activity monitor, **Actigraph GT9X** device, in the standard mail at their residence. After receiving the device, participants will engage in a telephone or virtual meeting with a research assistant to learn how to use the device. (approximately 30-40 minutes)
 - a. Participants will be asked to wear the activity monitor for 10 days prior to beginning the study. They will be asked to continuously wear the device on their wrist for the 10 days. Participants will return the device in a pre-paid envelope. (10 days) The same procedure will occur at the conclusion of the intervention for a post-intervention assessment. (10 days)

Orientation Session

All participants will participate in a virtual meeting with a research assistant that will welcome them to the study, review and reinforce the procedures and the technology that will be used. A review of WebEx, accessing the website and training videos, completing online surveys, and how to contact the research staff. Participants will then be administered a knowledge quiz by a research assistant. Finally, participants will be given the link and a the password to access the peer partner training videos on a website.

Peer partner training

There are a total of 11 videos (5-8 minutes in length) that participants will be asked to watch over a 2-week period. The total amount of time spent watching videos will be 55- 88 minutes. Participants can choose to complete watching these videos on their own schedule, in their self-selected environment. The videos will be available in Spanish and English.

The initial videos will cover topics on basic information about PD and exercise:

- a. What is Parkinson's disease?
- b. How can exercise help people with Parkinson's disease?
- c. What is the best type of exercise for people with Parkinson's disease?
- d. What is peer support?

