- e. How can I help someone else living with Parkinson's disease?

There will then be a synchronous virtual meeting that is led by the research team to review the content of the first 6 videos. (approximately 30 - 45 minutes)

The additional 6 videos will cover the following topics related to peer and social support:

- f. Active listening
- g. Creating SMART goals for exercise

- h. Checking in: getting feedback on exercise goals
- i. Identifying facilitators for exercise
- j. Problem-solving and overcoming barriers to exercise
- k. Family and community support for exercise

There will then be a second synchronous virtual meeting, led by the research team, to review the content of the last 6 videos to ensure comprehension and baseline knowledge. (approximately 30 - 45 minutes)

There will be a final synchronous meeting to review check-off sheets that will guide weekly discussions and a knowledge check will be completed through a brief quiz. (approximately 30 - 45 minutes)

Peer-supported mobile health physical activity intervention (*Compañeros con Parkinson's*)

All participants will be peer partners (supporters). Individuals will be matched with a peer of the same gender. Attempts will be made to match those with additional similar traits, such as age, physical activity level, work status, and country of origin. Participants in each matched pair will support one another as they both strive to improve their physical activity.

After participants have completed the training, they will receive a commercially available activity tracker (Fitbit Inspire 2) and instructions on its use. They will wear this activity tracker for the duration of the 8-week period except for showering/bathing. Peers will download the FitBit application on their smart phone or tablet. Participants will be asked to log in to the FitBit app daily to sync their data with the app. If they do not have a smartphone or tablet, one will be provided to them, along with a data plan for the duration of the study. They can choose to have assistance with downloading the app from a research assistant. They can receive basic training on its use with the support of a research assistant via a telephone call or virtual meeting.

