Participants will be asked to again wear the **Actigraph GTX9** for 10 days post-intervention, following the procedures noted for baseline assessment.

Focus group

After the 8-week intervention period is completed, participants will participate in one of 2 focus groups (10 participants per group) with a semi-structured interview format to further discuss acceptability, appropriateness, and feasibility. In addition, participants will discuss the cultural relevance of the intervention. The focus group will be held on a virtual meeting platform. Participants will have the choice to participate with their camera on or off. The discussion will be moderated by a research assistant. (Approximately 60 minutes)

A device/tablet/data plan for 3 months will be provided to participants, if they do not have one, so that they can participate in the study. We will ask participants to return the device/tablet at the conclusion of the study. We will provide them with a stamped and self-addressed envelope for the return of the device.

Length of subject's participation in the study including number of visits, frequency of visits, and length of visits: Participant's participation in the study will be via remote interactions. The number, frequency and length of sessions are noted above.

CONSENT PROCESS:

The informed consent process will occur either electronically or by standard mail combined with phone calls with the study team. Consent will be initiated, questions answered, and the informed consent form signed before any other study procedures are performed. The informed consent form will be signed electronically through a ReDCAP forms or via standard mail (with a provided self-addressed/stamped return envelope).

Consent Procedure: (Approximate time = 30 minutes) Potential participants who express interest in participating in the study and clear pre-screening questions will be provided with the option to provide informed consent electronically or to receive a hard copy of the consent to sign once received via standard mail. If electronic consent is selected, the participant will choose a time to speak with an authorized consenter to review and submit the form together while on the telephone.

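### The 3-month medication-stability window leaves almost no margin over the study's own 90 days of stated periods, and later changes in Parkinson medication are not recorded

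*Combined protocol and SAP*

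**What the plan says.** The Inclusion Criteria ask that a participant be "on a stable course of PD medications without any plans for change over the next 3 months". The list under Screening Procedures repeats the condition: "on a stable course of PD medications without any plans for change in the next 3 months". Both apply at the telephone stage, where the team will "conduct a pre-consent telephone eligibility screening to see if they qualify".

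The periods with a stated length come after that call:

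- Baseline Actigraph (baseline assessments, item 10a): "Participants will be asked to wear the activity monitor for 10 days prior to beginning the study".
- Peer partner training: videos "that participants will be asked to watch over a 2-week period".
- Intervention, which starts after training: "They will wear this activity tracker for the duration of the 8-week period except for showering/bathing".
- Post-assessment: the Actigraph is worn again "for 10 days post-intervention". The questionnaires are repeated by telephone when the intervention ends.

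Several required steps have no stated length in days: consent (electronic or by post, the postal route ending with a countersigned copy sent back before research activity starts), posting the Actigraph and the instruction call, orientation, the final training meeting, same-gender matching, and receipt of the Fitbit.

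Current medications are asked about at screening. The weekly staff call covers peer contact, barriers, technology and adverse events. The Post-assessment list has no medication item. The exploratory analysis is a set of paired t-tests in one group.

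**The concern.** A stability criterion in an uncontrolled pre-post study is useful to the extent that it spans both measurements. Here the clock starts at a call before consent, and the stated periods alone use up about three months. Any time spent on the untimed steps therefore moves the last measurements towards or past the end of the window.

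With no comparison group and no adjustment, a change in Parkinson medication between the two assessments cannot be told apart from an effect of the programme on activity, PDQ-39, GDS-15 or LARS. If the change is not recorded, it cannot even be described afterwards. The protocol does put some weight on these results: the sample size section expects them to show trends and early signs of efficacy and to inform later sample sizes, and the Dissemination paragraph says promising results would inform a randomized trial.

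**Working it through.** The protocol states no total duration, so there is no figure of its own to reproduce. The check adds up its stated periods.

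**Inputs from the protocol.** Baseline wear 10 days; training 2 weeks = 14 days; intervention 8 weeks = 56 days; post wear 10 days. The window is 3 months from the telephone screen, which is 89 to 92 days depending on the start date.

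**Input not in the protocol.** *g*, the total days taken by all untimed steps between the screen and the end of post wear. It is an assumption and is shown over a range.

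**Stated periods, no gaps.**
- End of intervention, when the questionnaires are due: 10 + 14 + 56 = day 80.
- Post wear: days 81 to 90, since 80 + 10 = 90.
- Margin at the end of post wear: 89 − 90 = −1 to 92 − 90 = +2 days.
- Margin at the questionnaires: 89 − 80 = 9 to 92 − 80 = 12 days.

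**Post-wear days outside a window of *w* days** = min(10, max(0, 90 + *g* − *w*)).

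| Assumed total gap *g* | Last day of post wear | Outside, *w* = 89 | Outside, *w* = 91 | Outside, *w* = 92 |
|---|---|---|---|---|
| 0 | 90 | 1 | 0 | 0 |
| 3 | 93 | 4 | 2 | 1 |
| 7 | 97 | 8 | 6 | 5 |
| 10 | 100 | 10 | 9 | 8 |
| 11 | 101 | 10 | 10 | 9 |
| 12 | 102 | 10 | 10 | 10 |
| 28 | 118 | 10 | 10 | 10 |

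For *w* = 91 and *g* = 7: 90 + 7 − 91 = 6 days. For *g* = 11: 90 + 11 − 91 = 10 days, the whole post-wear period.

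**Questionnaires.** They fall at about day 80 plus the gaps up to the end of the intervention. They leave the window when those gaps exceed *w* − 80: 9 days for *w* = 89, 11 for *w* = 91, 12 for *w* = 92. A delay in sending the Actigraph out a second time affects post wear but not the questionnaires.

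**Sensitivity to the order of periods.** If baseline wear ran alongside training, the total would be 14 + 56 + 10 = 80 days and the margin for post wear would be 9 to 12 days. The text places baseline wear before the study begins, so 90 days is the natural reading.

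**Window needed from the screen to cover everything:** 90 + *g*, so 104 days at *g* = 14 and 118 days at *g* = 28.

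**The case against.** The strongest reply is that on the stated figures the plan fits: 90 days lie within three months for most start dates. A reader might infer that the post measures will usually fall outside the window, or that the criterion fails to cover them at all. The documents do not support either. Both depend on delays whose length is nowhere given, and with no delay at most one wear day is outside. The questionnaires in particular keep 9 to 12 days of slack and would still be inside a 91-day window after a 7-day delay (about day 87).

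Some delays may also overlap or not count. The baseline interview can be done while the Actigraph is in the post, and nothing makes training wait for its return. A common start date for all participants might be inferred from the class sequence and the shared Fitbit group, but none is stated. The Focus group section offers a device and data plan for 3 months, which suggests that about three months of participation was intended.

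A further reply is that the criterion asks only about plans. An unplanned change on day 40 confounds as much as one on day 95, so extending the window by some days would do little by itself. This is right, and it makes recording actual changes the more important half of the remedy. Finally, a 20-person single-group study cannot isolate an intervention effect even with stable medication, and only the exploratory aim is involved. That limits the weight of the point without removing it.

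What remains is that the required untimed steps cannot plausibly total zero days, since the Actigraph goes by standard mail and recruitment extends to US territories. Stability is not reconfirmed after the screen, and later changes are not recorded.

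**Conclusion.** The point holds as one of margin and recording. The stated periods take 90 of 89 to 92 days, so a total delay of 0 to 3 days, depending on the calendar, is enough to put the end of post-intervention Actigraph wear outside the window. With 91 days, 6 of 10 wear days fall outside at an assumed 7-day delay and all 10 at 11 days or more. The questionnaires follow only beyond about 9 to 12 days. These sizes rest on the sequential reading of the periods and on assumed delays; the protocol gives no basis for saying how often they would occur.

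Separately, and whatever the delays, the criterion does not address unplanned changes and the plan has no step that would detect them. The consequence is limited to the exploratory pre-post comparisons. The thresholds for acceptability, appropriateness, feasibility and peer engagement are not affected. This is a cheap improvement, not a flaw in the study's main purpose.

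**What to change.** 1. State the study timeline in days from screening, including an allowance for consent, mailing, matching and scheduling.
2. Reconcile the eligibility window with it, so that the no-planned-change condition runs from the baseline assessment through the end of post-intervention Actigraph wear, and reconfirm it at the baseline interview.
3. Record actual changes in Parkinson medication, with dates, through the post-assessment, including the post-wear period. This concerns what is asked and recorded, not how anyone's medication is managed.
4. Report the exploratory pre-post comparisons descriptively, with and without participants whose medication changed, and give the number who changed.

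The cost is one revised eligibility sentence, a short question at baseline and again at post-assessment, and one additional descriptive comparison. A few people with changes planned shortly after three months may become ineligible. With 20 participants the comparison can show whether the pattern depends on those who changed, but cannot test it. The recording has to be in place before data collection ends, because changes not recorded then could be recovered only from recall or medical records.

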- **Aim 2: To determine the feasibility of a peer-supported mobile health physical activity intervention (*Compañeros con Parkinson's*) for exercise in Latinx people with PD.** We will examine: (2A) intervention engagement, as measured by attendance at exercise classes and with the number of peer contacts (2B) acceptability, (2C) appropriateness, (2D) feasibility and (2E) cultural relevance through self-report surveys and qualitative interviews with study participants.
- **Exploratory Aim: To determine the effects of the peer-supported mobile health physical activity intervention on physical activity** (objectively measured physical activity through the activity monitor), **motivation** (Behavioral Regulation in Exercise Questionnaire), **quality of life** (Parkinson Disease Questionnaire-39 (PDQ-39)), **depression** (Geriatric Depression Scale (GDS)), **apathy** (Lille Apathy Rating Scale (LARS)) and **self-efficacy for physical activity** (Self-Efficacy for Physical Activity (SEPA)).

Study Design: This is a prospective feasibility trial, single group pre-posttest design.

Sample size and justification

This study aims to enroll 20 participants. For this feasibility study, the sample size is comparable to other feasibility trials in populations of individuals with Parkinson disease (Lima & Rodrigues-de-Paula, 2013; Ellis et al., 2013, Colón-Semenza et al., 2018)^{17,19,20}. This sample size will allow for a comparison in feasibility, acceptability, and appropriateness within and across groups. This sample will allow for identifying trends and preliminary efficacy for this intervention. This study will help to inform an appropriate sample size to adequately power larger samples in future studies.

SELECTION AND ENROLLMENT OF PARTICIPANTS

Characteristics of the Study Population: We will recruit 20 Hispanic male, female or non-binary adults age 50+ with Parkinson's Disease. Participants must have the ability to speak, read and write in Spanish or English.

We will use the Recruitment and Community Engagement Core of the UConn Center on Aging. The Core provides a centralized infrastructure for the recruitment of older research volunteers from the community. Recruitment of subjects will be carried out by several mechanisms, Including:

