Content and thematic analysis of qualitative data; descriptive statistics to characterize the sample and measure feasibility.

- Aim 1 analysis
 - Scores equal to or greater than 75% on the Acceptability of Intervention Measure (AIM), Intervention Appropriateness measure (IAM), and Feasibility of Intervention Measure (FIM) are set to determine acceptability, appropriateness, and feasibility of the peer partner training.
 - Cultural relevance of the peer partner training will be determined through content analysis of focus group discussions
- Aim 2 analysis
 - Peer engagement will be successful if connecting $\geq 80\%$ of the recommended times over the course of the intervention period.
 - Scores equal to or greater than 75% on the Acceptability of Intervention Measure (AIM), Intervention Appropriateness measure (IAM), and Feasibility of Intervention Measure (FIM) are set to determine acceptability, appropriateness and feasibility of the peer partner intervention.
- Exploratory aim analysis
 - Group means will be compared from baseline to post-intervention using paired t-tests to assess change in physical activity levels (Physical Activity Scale for the Elderly & objectively measured physical activity through the activity monitor), motivation (Behavioral Regulation in Exercise Questionnaire), quality of life (Parkinson Disease Questionnaire-39 (PDQ-39)), depression (GDS), apathy (LARS) and self-efficacy for physical activity (Self-Efficacy for Physical Activity (SEPA)).

Dissemination: The results of this research will be disseminated at a professional conference in a poster or platform presentation. After receiving feedback from this presentation, results will be disseminated in a peer-

reviewed scholarly journal. Additionally, if the results from this research are promising, it will be used to inform a randomized controlled trial of the intervention.

PROTECTION OF HUMAN SUBJECTS

Risks to Human Subjects:

Physical Risk

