The FitBit data will be housed on the FitBit device and might be subject to a loss of confidentiality. Only those that have the email and password for the FitBit account will have access to this data. This data will be downloaded to an encrypted and password protected UConn computer during the course of the study. Once the study is over the password will be changed so that only the individual has access to their FitBit data.

Participants will be matched with another person with PD and communicate with this person once per week during a virtual meeting. Participants will be FitBit friends and see each other's steps per week. There is a risk of conflicts between the peer partners. One person in the peer pair may drop out of the study. We will attempt to create a successful match by matching peers with others with similar characteristics (age, retired

vs working, stage of the disease, etc.). If there is a conflict between peer partners, a research assistant will be available to meet with the pairs to help resolve the conflict. If a peer partner drops out, we will attempt to reassign the participant to another partner.

Other risks

Survey administration may make participants feel uncomfortable answering some of the questions. Participants will be instructed that they can choose not to answer any questions that make them feel uncomfortable.

References:

3. Alberts JL, Rosenfeldt AB. The Universal Prescription for Parkinson's Disease: Exercise. *J Parkinsons Dis*. 10(Suppl 1):S21-S27. doi:10.3233/JPD-202100

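### Feasibility is judged on post-intervention FIM scores with no stated denominator and no recruitment or retention measure, so it could be concluded from completers alone

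*Combined protocol and SAP*

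**What the plan says.** The research question, under Hypotheses or Research Question, Aims and Objectives, is whether the peer training and the peer-supported intervention are feasible in Latinx people with Parkinson disease. The analysis section offers "descriptive statistics to characterize the sample and measure feasibility" and then sets two kinds of numeric criterion.

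- **Survey scores.** The rule begins "Scores equal to or greater than 75% on the Acceptability of Intervention Measure (AIM" and covers IAM and FIM as well. It is applied to the training (Aim 1) and to the intervention (Aim 2), and FIM is the scale assigned to feasibility. The surveys are scheduled under Post-assessment.
- **Peer contact.** "Peer engagement will be successful if connecting" on at least 80% of the recommended occasions. The schedule is one call a week for 8 weeks.

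The aims also name training attendance, exercise-class attendance and a knowledge quiz, but the analysis section gives these no threshold and no analysis.

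On numbers: "This study aims to enroll 20 participants", justified because "the sample size is comparable to other feasibility trials in populations of individuals with Parkinson disease". On loss: "One person in the peer pair may drop out of the study", in which case the team will try to find the remaining person a new partner. On later use: "This study will help to inform an appropriate sample size to adequately power larger samples in future studies", and, if results are promising, "it will be used to inform a randomized controlled trial of the intervention".

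**The concern.** Whether eligible people will join and whether they will stay are central to feasibility, and the plan commits to reporting neither. The measure that settles feasibility is an opinion score taken at the end, when those who found the programme unworkable may already have gone. No rule says how people who leave before the post-assessment enter the 75% criterion, or whether that criterion refers to a mean score or to a share of participants.

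The gap matters more here because participants work in pairs: each loss also leaves a partner to be re-matched. The two focus groups of 10 add up to the full 20 enrolled, so they leave no room for loss. At stake are a favourable conclusion drawn from a selected subgroup, and a follow-on trial designed without a planned attrition or recruitment figure from this study.

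**Working it through.** **Plan's own figure.** The 20 rests on precedent. No alpha, power, effect size, SD, drop-out rate or precision target is given, so there is nothing to recompute.

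**Inputs.** From the documents: 20 enrolled, 8 weekly calls, thresholds of 75% and 80%. Assumed for illustration: 6 of 20 leave. The documents give no drop-out rate. I count calls per person, take the 8 weekly calls as the recommended contacts, and assume that those who stay are successfully re-paired when a partner leaves.

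**Step 1: retention.** 14/20 = 70%; exact (Clopper-Pearson) 95% CI 45.7% to 88.1%. For comparison:

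- 18/20 = 90% (68.3% to 98.8%)
- 16/20 = 80% (56.3% to 94.3%)
- 10/20 = 50% (27.2% to 72.8%)

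**Step 2: FIM rule.** Only people reached at post-assessment answer it. If the 14 score at least 75%, the criterion is met. If only 10 remain and do the same, it is met again. As written, the rule does not respond to the number lost.

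**Step 3: peer-contact rule.** With everyone enrolled counted there are 20 × 8 = 160 person-calls, and the bar is 0.80 × 160 = 128. With 14 finishing:

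| Case | Calls made | Denominator | Result |
|---|---|---|---|
| Leavers make no calls, finishers make all 8; all enrolled counted | 14 × 8 = 112 | 160 | 70%, fails |
| Leavers make 3 calls each, finishers make all 8; all enrolled counted | 112 + 6 × 3 = 130 | 160 | 81%, passes |
| Finishers make 7 of 8; only finishers counted | 14 × 7 = 98 | 14 × 8 = 112 | 87.5%, passes |
| Finishers make 7 of 8, leavers none; all enrolled counted | 98 | 160 | 61%, fails |

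With all enrolled counted and perfect finishers, the leavers must average (128 − 112)/6 = 2.7 calls for the rule to pass. If half are lost and the 10 finishers make 7 of 8 calls, the result is 70/80 = 87.5% on finishers, but 70/160 = 43.75% on all enrolled if the leavers made no calls.

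**Step 4: what a later trial would need.** The enrolment inflation factor is 1/retention: 1/0.90 = 1.11 and 1/0.70 = 1.43. For 100 evaluable participants that means 112 or 143 enrolled. The estimate from 20 people would itself be rough: the interval from Step 1 gives factors from 1/0.881 = 1.14 to 1/0.457 = 2.19, which is why the interval should be reported with the rate.

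**The case against.** Four objections deserve weight.

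1. *The peer-contact rule already guards against drop-out.* It does in part. If all 20 are counted and people leave before any call, losing more than four makes the rule fail. A reader might infer that a programme losing 30% of its participants would necessarily pass; the first row of the table shows otherwise. But the rule defines successful engagement rather than feasibility, its denominator is unstated, and later losses can pass even on the stricter count.
2. *The next trial can still be sized.* Correct. A reader might infer that the study cannot deliver what it promises on sample size, but the text says only that it will help to inform it. The paired pre-post data give a rough SD of change: with all 20 pairs, the 95% limits run from 0.76 to 1.46 times the estimate. The randomized trial is also conditional on promising results. What is missing is narrower: a planned attrition and recruitment estimate.
3. *The counts exist anyway.* Telephone screening, consent documentation and weekly staff calls should allow them to be recovered, and the general promise of descriptive statistics does not exclude them. Nothing, however, commits the study to reporting them or to using them in the conclusion.
4. *There is other feasibility evidence.* Attendance, the quiz and the focus groups are planned. The first two have no threshold or analysis, and the focus groups take place after week 8, with no provision for people who have left.

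**Conclusion.** The concern stands in limited form. The feasibility conclusion rests on post-intervention FIM scores, with peer contact judging engagement. Neither criterion states its denominator, and no recruitment or retention measure is planned. Feasibility could therefore be declared on finishers' answers at, for example, 70% retention (exact 95% CI 46% to 88%), while the peer-contact result moves between fail and pass on choices the plan leaves open. The 6 of 20 loss is an illustration, not a forecast: the documents list drop-out as a risk and give no rate.

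A reader might also infer that the plan's 80% contact threshold implies an 80% retention requirement. It does not, because contact frequency and retention measure different things. Such a bar would also discriminate poorly at this size, since 16/20 has an interval of 56% to 94%.

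The change should be made, because following the plan exactly can produce a conclusion that ignores those who left.

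**What to change.** In the Aim 2 analysis:

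- Report recruitment as consented/eligible, and as number consented per month.
- Report retention as participants completing both week 8 and the post-assessment, divided by all enrolled.
- Give exact 95% confidence intervals for both proportions and name both measures as feasibility outcomes.
- Compute the 80% peer-contact rule over all enrolled participants, and state whether the unit is the person or the pair.
- State whether the 75% rule refers to a mean score or to a share of participants. Report the FIM result together with the share of enrolled participants who answered, and do not conclude feasibility from finishers' scores alone.

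The investigators may pre-specify a retention target, for instance 80%, but should present it as their own judgement with its own reason.

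The cost is analysis wording and a few tabulated counts from screening, consent and weekly-call records. The downside is that the feasibility result may look less favourable.
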